## 8.4.1.4 Biomarker Endpoints

Biomarker endpoints are described in Section 4.2.4.5.

## 8.4.2 Safety Endpoints

Safety endpoints are described in Section 4.2.4.1.

## 8.5 Analysis Populations

Eligible subjects enter the study when the treatment allocation number is assigned by M.D. Anderson.

### 8.5.1 Efficacy Analysis Populations

The All Subjects as Treated (ASaT) population will be used for the analysis of ORR, DCR, TTP, PFS, and OS. The ASaT population consists of all allocated subjects who received at least one dose of study treatment.

The analysis population for DOR consists of responders (PR and CR).

Details on the approach to handling missing data are provided in Table 17.

### 8.5.2 Safety Analysis Populations

The ASaT population will be used for the analysis of safety data in this study. The ASaT population consists of all allocated subjects who received at least one dose of study treatment.

At least one laboratory or vital sign measurement obtained subsequent to at least one dose of study treatment is required for inclusion in the analysis of each specific parameter. To assess change from baseline, a baseline measurement is also required.

# Proprietary Information of MD Anderson

Protocol # 2016-0251

Date: February 24, 2020

113

## 8.6 Statistical Methods

### 8.6.1 Statistical Methods and Data Analysis

This section describes the statistical methods that address the primary and secondary objectives.

This is a single arm, open-label exploratory Phase II study. Since no effective treatments are available in this setting, a response rate of 15% (within 95% CI) is considered acceptable (i.e., the signal for launching further, larger studies with pembrolizumab in this patient population is  $\geq 1$  response in the current study). If no response is observed, the treatment with pembrolizumab will be considered ineffective. A total of 15 patients will be enrolled and treated to rule out a response rate of 15% or less with 90% power when at least one response is observed. In other words, with 15 patients treated, the probability of observing at least one response is more than 90% if the response rate is at least 15% (Table 16). Descriptive statistics including with 90% confidence interval will be computed. Observed response profile, clinical benefit rate at 6 months and PFS along with relevant confidence intervals will be used to guide future development decisions.

Table 16 Analysis Strategy for Efficacy Variables

Total evaluable patients	Number of responders	Response rate	Lower 90% CI*	Upper 90% CI*
15	0	0%	<1%	18%
15	1	7%	<1%	27%
15	2	13%	2%	36%
15	3	20%	6%	44%
15	4	27%	10%	51%
15	5	33%	14%	58%
15	6	40%	19%	64%
15	7	47%	24%	70%
15	8	53%	30%	76%
15	9	60%	36%	81%
15	10	67%	43%	86%
15	>10**	>67%	>43%	>86%

\* Exact confidence interval computed by the method of Clopper and Pearson (Biometrika 26:404-413, 1934)

\*\*Actual response rate with corresponding CI will be calculated. Exact confidence interval was calculated for all responses.

Kaplan-Meier method will be used to compute the survival rate for the time-to-event endpoints such as PFS. The efficacy in biomarker subgroups will be summarized by descriptive statistics.

Table 17 Statistical Methods Per Endpoint Analysis

Endpoint/Variable (Description, Time Point)	Statistical Method	Analysis Population	Missing Data Approach
Primary Endpoint			

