# Proprietary Information of MD Anderson

Protocol # 2016-0251

Date: February 24, 2020

22

Pharmaceuticals Inc.) to include the treatment of patients with hepatocellular carcinoma (HCC) who have been previously treated with sorafenib. Approval was based on an international, multicenter, randomized, double-blind, placebo-controlled trial of 573 patients with Child-Pugh A and Barcelona Clinic Liver Cancer Stage B or C HCC with documented disease progression following sorafenib. Patients were randomly allocated to receive regorafenib 160 mg orally once daily plus best supportive care (BSC) or matching placebo plus BSC for the first 21 days of each 28-day cycle (37). Treatment continued until disease progression or unacceptable toxicity. The trial demonstrated a significant improvement in overall survival (HR=0.63, 95% CI: 0.50, 0.79,  $p<0.0001$ ) with an estimated median overall survival for patients in the regorafenib arm of 10.6 months and 7.8 months for patients in the placebo arm. A statistically significant improvement was also demonstrated for progression-free survival (PFS) based on modified RECIST for HCC (HR=0.46, 95% CI: 0.37, 0.56,  $p<0.0001$ ), with an estimated median PFS of 3.1 and 1.5 months in the regorafenib and placebo arms, respectively. The overall response rate, based on modified RECIST, was 11% in the regorafenib arm and 4% in the placebo arm. The safety of regorafenib was evaluated in 1142 patients enrolled in randomized, placebo-controlled trials.

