In September 2017 the FDA granted accelerated approval to nivolumab the treatment of hepatocellular carcinoma (HCC) in patients who have been previously treated with sorafenib. Approval was based on a 154-patient subgroup of CHECKMATE-040 (95), a multicenter, open-label trial conducted in patients with HCC and Child-Pugh A cirrhosis who progressed on or were intolerant to sorafenib. In addition to including patients without active hepatitis viral infection, the trial enrolled patients with either active HBV (31%) or HCV (21%) but not those with active co-infection with HBV and HCV or with hepatitis D virus infection. Patients received nivolumab 3 mg/kg by intravenous infusion every 2 weeks. The confirmed overall response rate, as assessed by blinded independent central review using RECIST 1.1, was 14.3% (95% CI: 9.2, 20.8), with 3 complete responses and 19 partial responses. Response duration ranged from 3.2 to 38.2+ months; 91% of responders had responses lasting 6 months or longer and 55% had responses lasting 12 months or longer.

Despite these advances, continued investigation of additional agents for advanced HCC patients without a curative option remains crucial.

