## 4.3 Rationale

### 4.3.1 Rationale for the Trial and Selected Subject Population

#### Hepatocellular carcinoma

HCC is often driven by inflammation of various types, including viral infections. In a mouse model of HCC, blockade of PD-1 with immunostimulatory monoclonal antibodies extended survival (80). HCC patients with higher tumor expression of PD-L1 have a significantly poorer prognosis than patients with lower expression, and tumor expression of PD-L1 is also an independent predictor for postoperative recurrence in HCC (81). In addition, high expression levels of PD-1, both in TILs and peripheral blood mononuclear cells (PBMCs) also correlate with increased stage and recurrence in HCC patients after surgical resection (82). The interim analysis of a Phase I/II trial of nivolumab in patients with HCC demonstrated an estimated survival rate in evaluable patients (n=42) of 62% at 12 months with several durable responses. Responses were seen both in viral-mediated cancers and those without an underlying viral etiology. Results also showed the safety profile of nivolumab in HCC to be generally consistent with that previously reported in other tumor types and most recently, Nivolumab has been approved by FDA (83). Similarly, most recently, the FDA granted pembrolizumab (Keytruda) an accelerated approval for the treatment of patients with HCC who have previously received sorafenib based on findings from the phase II KEYNOTE-224 trial, in which single-agent pembrolizumab induced an overall response rate (ORR) of 17% (95% CI, 11-26) among 104 patients with advanced HCC previously treated with sorafenib (Zhu A, et al, Lancet Oncology 2018, PMID: 29875066). Among the 18 patients who responded, there was 1 complete response and 17 partial responses. Forty-six patients had stable disease, 34 patients had progressive disease, and 6 patients were not evaluable.

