## 4.3.2 HCV Disease and Selected Patient Populations

Chronic HCV infection is a major public health problem associated with a substantial medical, social and economic burden. According to the 2006 National Health and Nutrition Examination Survey (NHANES), the prevalence of antibodies to HCV in the US population is approximately 1.6% (84).

Despite the approval of several DAAs by the FDA, the great proportion of HCV infected patients remains undiagnosed as routine screening is not yet common in most countries, and infected patients may not have any symptoms for many years after being infected. It is thus predicted that in the next decade, the treatment naïve population may still be the largest patient population that will require therapy (85). Subjects with HCV GT1 and GT4, will be assessed in this study. Immunotherapy has been studied for the treatment of HCV infection and in chronic HCV patients with HCC. Single dose PD-1 antibody treatment (Nivolumab) was studied in patients with chronic HCV infection demonstrating viral load reduction with tolerable autoimmune side effects that included transaminitis (86). CTLA-4 blockade with tremelimumab showed efficacy against HCC and HCV with transaminitis noted most frequently after the first dose (87). However, treating HCV infection in the setting of active systemic therapy in HCC has not been studied to date. This approach may lead to improved HCC outcome in patients with concomitant HCV infection. Therefore we aim at combining pembrolizumab (FDA-approved secondline therapy in HCC) with anti-HCV, oral Zepatier in patients with HCV-related HCC.

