# Proprietary Information of MD Anderson

Protocol # 2016-0251

Date: February 24, 2020

111

Interim Analysis	No planned interim analysis for this Phase II study.
Multiplicity	No multiplicity adjustment is planned in this Phase II study.
Sample Size and Power	The planned sample size is 15 subjects per Arm

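### The one-response ORR signal in 8.6.1 rests on a premise that the protocol's own background contradicts, and meeting it would say nothing new about pembrolizumab or about adding Zepatier

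*Combined protocol and SAP*

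**What the plan says.** Section 8.6.1 gives the only decision rule for tumour response. It opens with "Since no effective treatments are available in this setting, a response rate of 15% (within 95% CI) is considered acceptable". It then defines the signal for larger studies with pembrolizumab as one or more responses in this study, and adds: "If no response is observed, the treatment with pembrolizumab will be considered ineffective". The size of 15 is supported by the statement that "the probability of observing at least one response is more than 90% if the response rate is at least 15" percent. Table 15 states: "The planned sample size is 15 subjects per Arm". Section 8.9 gives the same number.

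The background in the same version describes a different treatment setting:

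- Section 4.2.1.1 says that second-line HCC lacked a clear standard only until regorafenib was approved, reports a survival benefit for it, and continues: "The overall response rate, based on modified RECIST, was 11% in the regorafenib arm and 4% in the placebo arm".
- Section 4.2.1.1 also states: "In September 2017 the FDA granted accelerated approval to nivolumab the treatment of hepatocellular carcinoma (HCC) in patients who have been previously treated with sorafenib". The response rate it gives for nivolumab is 14.3% by RECIST 1.1.
- Section 4.3.1 reports accelerated approval of the study drug after sorafenib, because "single-agent pembrolizumab induced an overall response rate (ORR) of 17% (95% CI, 11-26) among 104 patients with advanced HCC previously treated with sorafenib".
- Section 4.3.2 calls pembrolizumab an approved second-line therapy. Of treating HCV during systemic HCC therapy, the basis of Arm B, it says: "This approach may lead to improved HCC outcome in patients with concomitant HCV infection".

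Section 2.1 notes that Zepatier has no known anti-cancer activity and that the arms are not meant to be compared directly.

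**The concern.** A rule that one response among 15 is a signal can be defended when nothing is known to work. It loses that defence when the drug under test already has a reported response rate in the same line of treatment. The background was updated for the three approvals; the statistical premise was not.

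This matters because the premise supports an operative rule, not just a narrative remark. In Arm A, the rule asks whether pembrolizumab shows any response, which Section 4.3.1 already answers. In Arm B, every subject receives pembrolizumab, so one response is the expected result whether or not Zepatier contributes anything. A report saying that the signal was met could then be read as new evidence in either arm when it is not.

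**Working it through.** **Inputs.** n = 15 per arm (Table 15, Section 8.9). Signal: at least one response (8.6.1). Candidate true rates: 15% (8.6.1); 4%, 11% and 14.3% (4.2.1.1); 17% with 95% CI 11 to 26 (4.3.1). Responses are treated as independent with a common rate p.

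**Formula.** P(signal) = 1 − (1 − p)^15.

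**The plan's own figure.** At p = 0.15: 1 − 0.85^15 = 0.913. The stated probability of more than 90% is correct, and 15 is the smallest sample size that reaches it.

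**The same rule at the rates cited in Section 4:**

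| True ORR | Source in the protocol | P(at least 1 of 15) |
|---|---|---|
| 4% | placebo, modified RECIST | 1 − 0.96^15 = 45.8% |
| 11% | regorafenib, modified RECIST | 1 − 0.89^15 = 82.6% |
| 14.3% | nivolumab, RECIST 1.1 | 1 − 0.857^15 = 90.1% |
| 17% | pembrolizumab alone | 1 − 0.83^15 = 93.9% |
| 11% to 26% | 95% CI of the pembrolizumab rate | 82.6% to 98.9% |

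The 4% is by modified RECIST, and the documents give no RECIST 1.1 placebo rate. As an assumed range for a nearly inactive treatment, the signal probability is 14.0% at p = 1%, 26.1% at 2% and 36.7% at 3%.

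**What each outcome would show.** Table 16 gives one response in 15 a 90% interval from below 1% to 27%, which contains all the rates above except those below its lower limit. Zero responses has an upper limit of 18%, which still includes 17%. If the true rate is 17%, zero responses occurs with probability 1 − 0.939 = 6.1%. Neither side of the rule separates the result from the published pembrolizumab rate.

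**Arm B.** If Zepatier has no effect on the tumour and the pembrolizumab rate is 17%, Arm B meets the signal with probability 93.9%. Any added effect could raise this by at most 100 − 93.9 = 6.1 percentage points, so the rule can hardly respond to one.

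**The case against.** Several points on the other side are sound.

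- **No comparator is named.** A reader might infer that 8.6.1 uses the wrong comparator. It states no null rate or historical control. The 15% is a target rate used to choose n, and it lies between the cited 14.3% and 17%, so correcting the premise would hardly move it. What is established is an outdated justification attached to a very low bar.
- **No claim about Zepatier is attached to the rule.** A reader might also infer a false positive claim for the combination in Arm B. Section 8.6.1 words the signal as one for studies with pembrolizumab, and Sections 2.1 and 5.3 disclaim comparing the arms. The efficacy primary in Arm B is SVR12, and improved HCC outcome is background rationale. The documents support only the weaker statement that meeting the signal is uninformative about that rationale.
- **Development decisions do not rest on one response alone.** Section 8.6.1 also cites the response profile, clinical benefit at 6 months and PFS, with confidence intervals. This softens the consequence, but the one-response signal remains in the text as a separate statement.
- **The cited rates are not fully like for like.** The 11% and 4% use modified RECIST, while this trial uses RECIST 1.1. The argument rests mainly on the 17%.

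It is also tempting to replace the rule with a threshold against 17%, such as 6 of 15, where the lower 90% limit in Table 16 is 19%. The documents do not support that. The 17% is itself uncertain: 6 or more responses occur with probability 3.0% if the true pembrolizumab rate is 17%, but 17.1% if it is 26%. No pembrolizumab response rate is given for HCV-positive HCC, the Arm B population. The chance of reaching 6 would be only 28% at a true rate of 30% and 60% at 40%.

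**Conclusion.** The point holds as an internal contradiction with a practical consequence. The statement that no effective treatments exist is inconsistent with Sections 4.2.1.1, 4.3.1 and 4.3.2 of the same version. The signal built on it occurs with probability 93.9% at the reported pembrolizumab rate (82.6% to 98.9% over its CI) and 45.8% at the cited placebo rate. Meeting it would neither add to the known pembrolizumab result in Arm A nor bear on whether Zepatier improves HCC outcome in Arm B.

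This rests on three assumptions: exactly 15 treated subjects per arm, where the plan says approximately; independent responses; and application of the 8.6.1 rule to each arm. The last follows from the per-arm sample size, since the text of 8.6.1 describes a single arm. The correction is worth making before results are reported, but the damage is limited: ORR is a secondary objective to be estimated (Section 3.2), and the primary endpoints in 8.4.1.1, safety and tolerability and SVR12, are unaffected.

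**What to change.** In Section 8.6.1:

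1. Delete the opening clause that says no effective treatments are available.
2. Cite the Section 4 rates as context: regorafenib 11% and placebo 4%, nivolumab 14.3%, pembrolizumab 17% (95% CI 11 to 26). Note that the 11% and 4% are by modified RECIST and that no pembrolizumab ORR for HCV-positive HCC is given.
3. Remove the statement that one or more responses is the signal for larger studies, and bring the companion sentence on zero responses into line.
4. Keep the probability of more than 90% for at least one response at a 15% rate only as the description of the sample size.
5. State that ORR in each arm is an estimate with its exact 90% CI, described alongside 17% (95% CI 11 to 26), and that responses in Arm B are not by themselves evidence of an added effect of Zepatier.
6. Do not put a superiority threshold in place of the signal.

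The cost is wording only, with no added subjects or procedures. The downside is a less favourable ORR claim: the trial could no longer report a positive signal on one response.

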## 7.1.4.1.2 Tumor Imaging During the Trial

The first on-trial imaging assessment should be performed at 9 weeks (63 days  $\pm$ 7 days) from the date of allocation. Subsequent tumor imaging should be performed Q9W (63 days  $\pm$ 7 days) or more frequently if clinically indicated. Imaging timing should follow calendar days and should not be adjusted for delays in cycle starts. Imaging should continue to be performed until disease progression or notification by Merck, whichever occurs first. All supplemental imaging, done outside from M.D. Anderson, must be submitted to M.D. Anderson radiology for retrospective review.

Per RECIST 1.1, PR and CR should be confirmed by a repeat tumor imaging assessment obtained 4 weeks or longer from the date the response was first documented. The tumor imaging performed to confirm a response may be performed, at the earliest, 4 weeks after the first indication of a response, or at the next scheduled scan (ie, 9 weeks later), whichever is clinically indicated. Subjects will then return to regular scheduled imaging Q9W (63 days  $\pm$ 7 days), starting with the next scheduled imaging time point. Subjects who obtain a confirmation scan do not need to undergo the next scheduled tumor imaging if it is 4 weeks later; tumor imaging may resume at the subsequent scheduled imaging time point.

Per iRECIST (Section 7.1.4.1.5), disease progression should be confirmed by the site 4 to 8 weeks after site-assessed first radiologic evidence of PD in clinically stable subjects. Subjects who have unconfirmed disease progression may continue on treatment at the discretion of the site Investigator until progression is confirmed by the site provided they have met the conditions detailed in Section 7.1.4.1.5. Subjects who receive confirmatory imaging do not need to undergo the next scheduled tumor imaging if it is less than 4 weeks later; tumor imaging may resume at the subsequent scheduled imaging time point if clinically stable. Subjects who have confirmed disease progression by iRECIST, as assessed by the site, will discontinue trial treatment. Exceptions are detailed in Section 7.1.4.1.5.

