#### 8.4.1.2 Secondary Exploratory/Efficacy Endpoints

- ORR is defined as the proportion of the subjects in the analysis population who have a CR or PR. Responses are based on assessments by the blinded M.D. Anderson radiology per RECIST 1.1
- DOR is defined as the time from first response to disease progression in subjects who achieve a PR or better, based on assessments by the blinded M.D. Anderson radiology per RECIST 1.1.
- DCR is defined as the percentage of subjects who have achieved confirmed CR or PR or have demonstrated SD for at least 24 weeks prior to any evidence of progression, based on assessments by the blinded M.D. Anderson radiology per RECIST 1.1
- TTP is defined as the time from randomization to the first documented disease progression. If there is no documented disease progression, TTP is censored at last

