## 8.9 Sample Size

In this study, approximately 15 subjects will be enrolled per Arm.

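### Section 8.6.1: at least one response in 15 does not rule out a response rate of 15% or less; the 90% figure is the chance of seeing a response when the rate is 15%

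*Combined protocol and SAP*

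**What the plan says.** Section 8.6.1 calls a 15% response rate acceptable and takes one or more responses as the signal to launch larger studies. For the opposite result it says: "If no response is observed, the treatment with pembrolizumab will be considered ineffective". It then justifies the number of patients, who are enrolled "to rule out a response rate of 15% or less with 90% power when at least one response is observed". The next sentence, offered as a restatement, says that with 15 patients the chance of at least one response exceeds 90% if the rate is at least 15%. Table 16 lists exact 90% Clopper-Pearson intervals for 0 to 10 responders.

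Section 8.9 adds only the number: "In this study, approximately 15 subjects will be enrolled per Arm". The paragraph in 8.6.1 opens with a premise, "Since no effective treatments are available in this setting". Section 4.3.1, however, reports that "single-agent pembrolizumab induced an overall response rate (ORR) of 17" percent (95% CI 11 to 26) in sorafenib-treated patients.

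**The concern.** Section 8.6.1 treats its two justifying sentences as equivalent, and they are not. The second is about how likely a response is when the drug has a 15% rate, so 15% is the target rate. The first claims that seeing a response excludes 15% and everything below it, so 15% becomes the rate to be rejected. The same figure cannot serve both purposes under a one-response threshold.

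This is the only place where the plan gives an efficacy reason for 15 patients. If it stands, a report could say, citing the plan, that a single response excluded a rate of 15% or less. It could also say that no response showed the drug to be ineffective, although the plan's own interval remains compatible with the rate the protocol cites for the same drug.

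**Working it through.** **Inputs.** n = 15 (8.6.1, 8.9); reference rate 15% (8.6.1); two-sided 90% Clopper-Pearson intervals (Tables 15 and 16); cited pembrolizumab ORR 17% (4.3.1). The 5% and 10% rates are illustrative. Responses are taken as independent with a common probability p.

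**1. Reproduce the plan's figure.** P(at least one response) = 1 − (1 − p)^15.
- p = 15%: 1 − 0.85^15 = 1 − 0.087 = 0.913
- With n = 14: 1 − 0.85^14 = 0.897

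The statement of more than 90% is therefore correct, and 15 is the smallest n that meets it.

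**2. Ask whether that is power to rule out 15%.** If 15% is the rate to be ruled out, 0.913 is the probability of meeting the rule when that rate is true. It is a false-positive rate. At lower true rates the rule is met with probability:
- p = 10%: 1 − 0.90^15 = 0.794
- p = 5%: 1 − 0.95^15 = 0.537

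**3. Exact 90% intervals, 5% in each tail.** The lower limit L solves P(X ≥ x | L) = 0.05; the upper limit U solves P(X ≤ x | U) = 0.05.

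| Responders | Computed 90% CI | Table 16 |
|---|---|---|
| 0/15 | 0 to 18.1% | <1% to 18% |
| 1/15 | 0.3% to 27.9% | <1% to 27% |
| 5/15 | 14.2% to 57.7% | 14% to 58% |
| 6/15 | 19.1% to 64.0% | 19% to 64% |
| 10/15 | 42.3% to 85.8% | 43% to 86% |

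One response leaves 15% well inside the interval. The lower limit first exceeds 15% at 6/15. At two-sided 95% the lower limits are 11.8% for 5/15 and 16.3% for 6/15, so the requirement is again 6/15. The lower limit for 1/15 is below 1% whether the interval is 80%, 90% or 95%.

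**4. What ruling out 15% would take with 15 patients.** P(X ≥ 6 | n = 15, p = 0.15) = 0.0168. A rule of six or more has power of 28% at a true rate of 30% and 60% at 40%. It reaches 90% only at a true rate of about 53%.

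**5. Zero responses.** U = 1 − 0.05^(1/15) = 18.1%, above both 15% and 17%. P(0/15) = 0.85^15 = 8.7% at 15%, and 0.83^15 = 6.1% at 17%.

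**6. Table 16.** Recomputing the rows for 0 to 10 responders finds two cells that do not round to the printed value: the upper limit for 1/15 (27.9%, printed 27%) and the lower limit for 10/15 (42.3%, printed 43%). The last row carries the 43% forward.

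**7. The premise.** Section 4.2.1.1 describes the approval of regorafenib after sorafenib with a survival benefit, and the accelerated approval of nivolumab with a 14.3% response rate. Section 4.3.1 reports accelerated approval of pembrolizumab, and 4.3.2 calls it an approved second-line therapy. The opening clause of 8.6.1 contradicts all of these.

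**The case against.** The strongest defence is that the plan's next sentence states the correct property, that 15 is the right n for it, and that the study is exploratory with tolerability and SVR12 as primary endpoints. All of that stands. It lowers the consequence, but it does not make the first sentence true.

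A reader might infer more than the documents support:
- *The sample size is miscalculated.* It is not; 15 is the smallest n giving more than 90% at a 15% rate.
- *The zero-response rule is invalid.* This depends on the confidence level. A one-sided 90% upper limit for 0/15 is 1 − 0.10^(1/15) = 14.2%, below 15%, so the rule is coherent as a futility screen with 8.7% false-negative risk. What fails is the flat verdict of ineffectiveness beside a tabulated upper limit of 18%.
- *These thresholds alone decide development.* Section 8.6.1 also uses the response profile, clinical benefit at 6 months and PFS, with confidence intervals.
- *A single unconfirmed response could trigger the signal.* In 8.4.1.2, "ORR is defined as the proportion of the subjects in the analysis population who have a CR or PR", without the word confirmed. But 7.1.4.1.2 says that "PR and CR should be confirmed by a repeat tumor imaging assessment obtained 4 weeks or longer" after first documentation, and 4.3.4.2 includes confirmatory assessment in the ORR definition. The gap is one of harmonisation.
- *The rule should be judged against the 4% placebo rate.* The probability of a signal at 4% is 1 − 0.96^15 = 46%. Section 4.2.1.1, however, says: "The overall response rate, based on modified RECIST, was 11% in the regorafenib arm and 4% in the placebo arm". This trial's ORR uses RECIST 1.1, so 4% is not a matched benchmark. The 5% and 10% figures make the point without it.
- *Both thresholds should be removed.* Keeping a screen is a design choice; only its description is wrong.

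**Conclusion.** The statement that at least one response in 15 rules out a rate of 15% or less with 90% power is false. The correct property is a 91% chance of at least one response at a true rate of 15%, falling to 79% at 10% and 54% at 5%. One response leaves 0.3% to 27.9% open; excluding 15% takes six. On the plan's own intervals, no response excludes neither 15% nor 17%. It can support a decision to stop, at a stated risk of 8.7% or 6.1%, but not a conclusion that the drug is ineffective.

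The figures assume exactly 15 treated subjects and independent responses. Enrolment is approximate and subjects are not replaced (5.7), so with 14 the chance at 15% would be 89.7%. The finding about one response does not depend on the interval level; the finding about zero responses does, and is made at the two-sided 90% level the plan tabulates. Severity is moderate.

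**What to change.** In 8.6.1:
- Replace the sentence containing the claim with: *With 15 treated subjects the probability of at least one response is 91% if the true ORR is 15%, 79% at 10% and 54% at 5%; the design does not rule out an ORR of 15% or less.*
- Describe one or more responses as a minimal-activity screen. Describe 0/15 as a futility screen with a false-negative risk of 8.7% at a true ORR of 15% (6.1% at 17%), in place of the verdict of ineffectiveness. Interpret the ORR with its exact 90% interval.
- Delete the premise that no effective treatments are available.
- In Table 16, change the 1/15 upper limit to 28% and the 10/15 lower limit to 42%, and the last row from >43% to >42% so that it follows the corrected row.
- Align the reference to a 95% interval with the 90% intervals used elsewhere in the section.

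Adding the word confirmed to the ORR definition in 8.4.1.2, to match 4.3.4.2 and 7.1.4.1.2, is worth doing at the same time as harmonisation only.

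The cost is an amendment to wording and a few table entries. The stated operating characteristics will look less favourable. The sample size and interval method do not change.
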